## **9.3 Ethics and regulatory review**

An Ethics Committee must approve the final study protocol, including the final version of the Informed Consent Form(s) and any other written information to be provided to the patients. The Investigator will ensure the distribution of these documents to the applicable Ethics Committee, and to the study site staff.

[figure not shown]
The opinion of the Ethics Committee must be given in writing. The Investigator must submit the written approval to AstraZeneca before enrolment of any patient into the study.

The Ethics Committee must approve all advertising used to recruit patients for the study.

AstraZeneca must approve any modifications to the Informed Consent Form that are needed to meet local requirements.

If required by local regulations, the protocol must be re-approved by the Ethics Committee annually.

Before enrolment of any patient into the study, the final study protocol, including the final version of the Informed Consent Form, is approved by the national regulatory authority or a notification to the national regulatory authority is done, according to local regulations.

The distribution of any of these documents to the national regulatory authorities will be handled by AstraZeneca.

AstraZeneca is responsible for informing the Regulatory Authority of SAEs/SUSARs as per local country regulations and guidelines. AstraZeneca will be responsible for safety regulatory reporting.

For all countries except the US and Canada, AstraZeneca will provide Regulatory Authorities, Ethics Committees and Principal Investigators with safety updates/reports according to local requirements. For the US and Canada, each Principal Investigator is responsible for providing the Ethics Committees/IRB with reports of any serious and unexpected adverse drug reactions from any other study conducted with the investigational product. AstraZeneca will provide this information to the Principal Investigator.

#### **9.4 Informed consent**

The Principal Investigator(s) at each centre will:

- Ensure that the patient is given full and adequate oral and written information about the nature, purpose, possible risk and benefit of the study;
- Ensure that the patients are notified that they are free to discontinue from the study at any time;
- Ensure that the patient are given the opportunity to ask questions and allowed time to consider the information provided;
- Obtain and document the patient's signed and dated informed consent before conducting any procedure specifically for the study;
- Ensure the original, signed Informed Consent Form is stored in the Investigator's Study File;
- Ensure a copy of the signed Informed Consent Form is given to the patient.

#### **9.5 Changes to the protocol and informed consent form**

Study procedures will not be changed without the mutual agreement of the Co-ordinating Investigator and AstraZeneca.

If there are any substantial changes to the study protocol, then these changes will be documented in a study protocol amendment. If required a new version of the study protocol (Amended Protocol) will be written.

The amendment must be approved by each Ethics Committee and if applicable, also the national regulatory authority, before implementation. Local requirements must be followed for amended protocols.

AstraZeneca will distribute any subsequent amendments and new versions of the protocol to each Principal Investigator(s). For distribution to Ethics Committee see Section 9.3.

If a protocol amendment requires a change to a centre's Informed Consent Form, AstraZeneca and the centre's Ethics Committee must approve the revised Informed Consent Form before the revised form is used.

If local regulations require, any administrative change will be communicated to or approved by each Ethics Committee.

## **9.6 Audits and inspections**

Authorized representatives of AstraZeneca, a regulatory authority, or an Ethics Committee may perform audits or inspections at the centre, including source data verification. The purpose of an audit or inspection is to systematically and independently examine all study-related activities and documents, to determine whether these activities were conducted, and data were recorded, analysed, and accurately reported according to the protocol, GCP, guidelines of the ICH, and any applicable regulatory requirements. The Investigator will contact AstraZeneca immediately if contacted by a regulatory agency about an inspection at the centre.

## **10. STUDY MANAGEMENT BY ASTRAZENECA (OR DELEGATE)**

### **10.1 Pre-study activities**

Before the first patient is entered into the study, it is necessary for a representative of AstraZeneca to visit the investigational study site to:

- Determine the adequacy of the facilities;
- Discuss with the Investigator(s) (and other personnel involved with the study) their responsibilities with regard to protocol adherence, and the responsibilities of AstraZeneca or its representatives. This will be documented in a Clinical Study Agreement between AstraZeneca and the Investigator.

### **10.2 Training of study site personnel**

Before the first patient is entered into the study, an AstraZeneca representative will review and discuss the requirements of the Clinical Study Protocol and related documents with the investigational staff and also train them in any study specific procedures utilised. They will also discuss the procedures associated with the collection of samples and mandatory biomarker research with a representative of AstraZeneca. The requirements for the collections of the patients' sample will also be made clear.

The Principal Investigator will ensure that appropriate training relevant to the study is given to all of these staff, and that any new information relevant to the performance of this study is forwarded to the staff involved.

The Principal Investigator will maintain a record of all individuals involved in the study (medical, nursing and other staff).

### **10.3 Monitoring of the study**

During the study, an AstraZeneca representative will have regular contacts with the study site, including visits to:

- Provide information and support to the Investigator(s);
- Confirm that facilities remain acceptable;
- Confirm that the investigational team is adhering to the protocol that data are being accurately and timely recorded in the CRFs, and that investigational product accountability checks are being performed;
- Perform source data verification (a comparison of the data in the CRFs with the patient's medical records at the hospital or practice, and other records relevant to the study) incl. verification of informed consent of participating patients. This will require direct access to all original records for each patient (eg, clinic charts);
- Ensure withdrawal of informed consent to the use of the patient's biological samples is reported and biological samples are identified and disposed/destroyed accordingly, and the action is documented, and reported to the patient.

The AstraZeneca representative will be available between visits if the Investigator(s) or other staff at the centre needs information and advice about the study conduct.

#### **10.3.1 Source data**

Refer to Clinical Study Agreement for location of source data.

### **10.4 Study agreements**

The Principal Investigator at each centre must comply with all the terms, conditions, and obligations of the Clinical Study Agreement for this study. In the event of any inconsistency between this Clinical Study Protocol and the Clinical Study Agreement, the Clinical Study Protocol shall prevail.

Agreements between AstraZeneca and the Principal Investigator must be in place before any study-related procedures can take place, or patients be enrolled.

## 10.5 Study timetable and end of study

The study is expected to start in October 2008 and the PK Phase to be completed by end of February 2009. The Continued Supply Expansion Phase is expected to be completed by Q2 2014.

The end of this study is defined as the date of the last visit of the last patient, occurring when all patients have completed study therapy.

For patients in the PK phase (cohorts 1 and 2) and Groups 1-7 data collection will continue until both the following criteria have been met:

[figure not shown]
- all gBRCA Group 1, 6 and 7 patients have progressed as per RECIST or AstraZeneca has determined that sufficient efficacy data has been collected
- all patients continuing on treatment have been assessed for safety for a minimum of 6 cycles (1 cycle being 28 days) or all patients have discontinued study treatment, whichever is the earlier.

When the above criteria are met the clinical database will be closed and only SAE data and investigator's assessment of response will be collected. All patients in the PK phase (cohorts 1 - 3) and Groups 1-7 can continue to receive study treatment until they meet any discontinuation criteria as per Section 5.5.1. Once all patients have completed 6 cycles, all protocol assessments can be stopped and patients should attend clinic visits according to routine clinical practice, approximately every 6-8 weeks. SAEs will continue to be reported to AstraZeneca in the usual way for patients who continue on AZD2281 until 30 days after study treatment is discontinued and followed-up as outlined in Section 5.5.2. Drug accountability should continue to be performed until the patient stops study treatment completely.

For patients in Group 8 all data will be collected in the clinical database up to and including Cycle 6 for each patient. For patients continuing past Cycle 6 only AEs, SAEs, concomitant medication, laboratory data, dosing information will be collected in the database. Investigator's assessment of response will be assessed but not collected in the clinical database. All other protocol assessments do not need to be performed

For patients in Group 8 all data collection will continue until both the following criteria have been met:

- all Group 8 patients have progressed as per RECIST or AstraZeneca has determined that sufficient efficacy data has been collected
- all Group 8 patients continuing on treatment have been assessed for safety for 12 cycles (or AstraZeneca has determined that sufficient safety data has been collected), or all patients have discontinued study treatment, whichever is the earlier.

When the above criteria are met the clinical database will close to new data. All patients in Group 8 can continue to receive study treatment until they meet any discontinuation criteria as per Section 5.5.1. Once the criteria above have been met and the database closed, all protocol assessments can be stopped and patients should attend clinic visits according to routine clinical practice, approximately every 6-8 weeks. SAEs will continue to be reported to AstraZeneca in the usual way for patients who continue on AZD2281 until 30 days after study treatment is discontinued and followed-up as outlined in Section 5.5.2. Drug accountability should continue to be performed until the patient stops study treatment completely.

The study may be terminated at individual centres if the study procedures are not being performed according to GCP, or if recruitment is slow. AstraZeneca may also terminate the entire study prematurely if concerns for safety arise within this study or in any other study with AZD2281.

## **11. DATA MANAGEMENT BY ASTRAZENECA OR DELEGATE**

Data should be recorded in English onto the CRFs in black ink. Any corrections should be made legibly and initialled and dated by approved personnel (correction fluid or covering labels must not be used).

CRFs will be double data-entered into the study database, and the data will be checked for missing, invalid or inconsistent data points. Data queries arising from these checks will be sent to the Investigator for response and signature.

Once all data queries have been resolved, the study will be declared to be “clean”, and the study database will be locked ready for statistical analysis.

Data associated with biological samples will be transferred to laboratories internal or external to AstraZeneca.

## **12. EVALUATION AND CALCULATION OF PHARMACOKINETIC, PHARMACODYNAMIC, SAFETY AND STATISTICAL ANALYSIS BY ASTRAZENECA**

### **12.1 Pharmacokinetic/Pharmacodynamic evaluation**

#### **12.1.1 Calculation or derivation of Pharmacokinetic variables**

The PK analyses of the AZD2281 plasma concentration data will be performed by (or on behalf of) Clinical Pharmacology & DMPK, Alderley Park, AstraZeneca.

For the PK Phase, non-compartmental methods will be used for the evaluation of the AZD2281 plasma concentration-time data for each subject on each dosing occasion. The maximum plasma concentration ( $C_{max}$ ) and the time of the maximum concentration ( $t_{max}$ ) will be determined by visual inspection of the concentration-time profiles. Where possible the

terminal rate constant ( $\lambda_z$ ) will be calculated by log linear regression of the terminal portion of the concentration-time profiles. Where there are sufficient data, the terminal half-life ( $t_{1/2}$ ) will be calculated as  $\ln 2/\lambda_z$ . The area under the plasma concentration-time curve up to the last quantifiable sample ( $AUC_{(0-t)}$ ) will be calculated using the linear trapezoidal rule and, where appropriate,  $AUC_{(0-t)}$  will be extrapolated to infinity using  $\lambda_z$  to obtain AUC. The apparent clearance (CL/F) will be determined from the ratio of dose/AUC. The apparent volume of distribution ( $V_z/F$ ) will be calculated by dividing dose by ( $AUC \times \lambda_z$ ).

For the patients in Group 1 of the Continued supply phase, non-linear mixed effects modelling will be used for the evaluation of the AZD2281 steady state plasma concentration-time data to determine the maximum steady state drug concentration in the plasma during the dosing interval ( $C_{ss,max}$ ), the minimum steady state drug concentration in plasma ( $C_{ss,min}$ ) and the area under the plasma concentration-time curve during the dosing interval at steady state (AUCss). For those patients in Group 2, non-compartmental methods will be used for the evaluation of the steady state plasma concentration-time data to determine  $C_{ss,max}$ ,  $C_{ss,min}$  and AUCss for both the Melt Extrusion (tablet) formulation and the Gelucire® 44/14 (capsule) formulation. For the patients in Groups 3 to 8 non compartmental methods will be used to determine single dose  $C_{max}$ ,  $C_{min}$  and  $AUC_{0-8}/AUC_{0-12} / AUC_{0-24}$  and non-linear mixed effects modelling will be used to determine steady state  $C_{ss,max}$ ,  $C_{ss,min}$ , and AUCss.

## **12.2 Calculation or derivation of safety variable(s)**

### **12.2.1 Other significant adverse events (OAE)**

During the evaluation of the AE data, an AstraZeneca medically qualified expert will review the list of AEs that were not reported as SAEs and discontinuations due to AEs (DAEs). Based on the expert's judgement, significant AEs of particular clinical importance may, after consultation with the Global Safety Physician, be considered OAEs and reported as such in the Clinical Study Report.

Examples of these may be marked haematological and other laboratory abnormalities and certain events that lead to intervention (other than those already classified as serious), dose reduction or significant additional treatment.

## **12.3 Calculation or derivation of efficacy variable(s)**

A secondary objective of the Continued Supply Expansion Phase is to summarise the efficacy of AZD2281 on patients who receive tablet compared to patients who receive capsules. This will be achieved by measuring the % change in tumour burden compared with baseline, Best Objective Response, PFS and CA-125 response. Analyses will be performed in the overall population and in the gBRCA ovarian cancer subgroup.

The RECIST criteria will be used to programmatically determine % change in tumour burden compared with baseline, Best Objective Response and PFS.

### **12.3.1 Change from baseline in the sum of target lesions**

This will be determined by calculating the % change in tumour burden, determined from the sum of longest diameters in target lesions measured per RECIST, at each follow-up tumour assessment compared with baseline.

### **12.3.2 Best Overall Response (by RECIST)**

Categorisation of best overall response will be based on the RECIST criteria (Appendix F) using the following response categories: complete response (CR), partial response (PR), stable disease (SD) and progressive disease (PD). Best overall response will be calculated as the best response recorded from date of enrolment (taking as reference for progressive disease the smallest measurements recorded since the treatment started) for each patient, and will be used for the summaries of objective response. Best overall response will be determined programmatically based on the RECIST criteria.

A best overall response of CR means that a response of CR is recorded at one visit and confirmed by repeat imaging at the next scheduled visit. A CR that was not confirmed because the next scheduled scan was after the data cut-off will be counted as a CR. Similarly for PR. In the case of SD, follow-up measurements must have met the SD criteria for a minimum interval of 7 weeks after randomisation.

### **12.3.3 Progression Free Survival**

PFS is defined as the time from randomisation to the earlier date of assessment of objective progression (per RECIST criteria) or death by any cause in the absence of progression. Patients without a progression event and still alive at the time of analysis will be censored at the time of their last evaluable objective tumour assessment. This includes patients who are lost to follow up or who withdraw consent.

If at any follow-up visit  $> 1/3$  of the target lesions recorded at baseline are missing then target lesion response will be not-evaluable (NE) (unless the sum of the longest diameters [LDs] of non-missing target lesion LDs would result in PD).

If  $\leq 1/3$  of lesions recorded at baseline are missing then the results will be scaled up (based on the baseline sizes) to give an estimated sum of diameters and this will be used in calculations.

A complete response will not be permissible at a visit response where there is missing data.

Objective progression is defined as at least a 20% increase in sum of longest diameters of the target lesions (compared to previous minimum sum) or an overall non-target lesion assessment of progression or a new lesion.

Patients are to have radiological scans until objective progression, regardless of whether they discontinue their randomised therapy or take another anti cancer therapy prior to progression.

Tumour assessments for Group 8 patients should be stopped after Cycle 5 (week 16). Dates of progression and death will be defined as follows:

- The actual date of progression will be used in the analysis regardless of whether the patient had previously discontinued all or part of their randomised therapy, started another anti cancer therapy, the event occurred between scheduled visits or previous

visits were not evaluable due to partially, or completely missing tumour assessments. This also applies to patients who die in the absence of progression.

- If radiological assessments take place on multiple dates at a visit then the date of progression used for analysis will be the earliest of target lesions or non-target lesion or new lesion dates, regardless of which component contributed to progression.

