### **Investigating different tablet schedules (Group 8)**

The primary objective of the randomised tablet formulation continued supply expansion phase is to determine the safety and tolerability profile of selected dose schedules of the melt-

extrusion (tablet) formulation. No formal statistical comparisons of safety data will be performed. Instead, data will be listed and summarised descriptively by dose schedule.

The secondary objectives of the randomised tablet formulation continued supply expansion phase will involve:

[figure not shown]
- All patients from Group 8 contributing to an assessment of the single dose and steady state exposures of AZD2281 achieved with selected tablet dose schedules. Plasma concentration data and PK parameters will be listed and summarised descriptively using the appropriate standard summary statistics.
- To describe the efficacy data observed in patients treated with the Melt-extrusion (tablet) formulation. Summaries and waterfall plots of percentage change from baseline in sum of target lesions will be presented, and this data will also be analysed by analysis of covariance fitting baseline sum of target lesions as a continuous covariate and treatment group as a factor. Summary statistics will be presented for best overall response according to RECIST. PFS will be summarised using Kaplan-Meier estimates over time and will be displayed graphically. Analyses will be performed in the overall population.
- To obtain a preliminary assessment of the effect of food on the exposure of AZD2281.

[figure not shown]

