- d AEs must be collected from the time of informed consent, throughout the treatment period and up to and including the follow-up period. All ongoing AEs must be monitored until resolution unless, in the Investigator's opinion, the condition is unlikely to resolve due to the patient's underlying disease. After discontinuation from treatment, patients must be followed up for all existing and new AEs for 30 calendar days (if SAEs, they must be reported to AstraZeneca within 24 hours) and followed until resolution unless, in the opinion of the Investigator, the condition is unlikely to resolve due to the patient's underlying disease.
- e For all patients enrolled into Groups 3 to 7 blood samples will be collected on Day 1 at the following timepoints: Pre-dose, 0.25, 0.5, 1, 1.5, 2, 3, 4, 6, 8, 10, 12 hours after morning dosing and on day 8 and Day 15 at the following timepoints: Pre-dose and 1 hour after morning dosing.
- f For the additional patients that are recruited to Groups 3 onwards, blood samples will be collected on Day 29 at the following timepoints: pre-dose and post-dose between 0 - 0.5 hours, 0.5 to 1.5 hours, 1.5 - 3 hours, 3 - 6 hours, 6 - 8, and 8-12 hours.
- g For the additional patients that are recruited to Group 6 and 7, blood samples will be collected on Day 29 and Day 57 at the following timepoints: pre-dose and post-dose between 0 - 0.5 hours, 0.5 to 1.5 hours, 1.5 - 3 hours, 3 - 6 hours, 6 - 8, and 8-12 hours.
- h For the additional patients recruited to Group 6, 7 and 8, follow-up tumour assessments will be performed every 8 weeks (+/-1 week) until disease progression or study end (Tumour assessments for Group 8 patients should be stopped after Cycle 5). Any other sites at which new disease is suspected should also be appropriately imaged. If scans are performed outside of scheduled visit  $\pm$  1 week window interval and the patient has not progressed, every attempt should be made to perform the subsequent scans at their scheduled time points. Patients must be followed until progression regardless of whether study treatment is discontinued or delayed and/or protocol violation. A repeat scan is needed at the next scheduled tumour assessment (at least  $\geq$  4 weeks) for confirmation of a PR or CR by RECIST. Radiological examinations performed in the conduct of the study should be retained at site as source data and may be collected by the sponsor if required.

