- Tumour marker CA-125 will be assessed locally from blood samples taken at screening, visit 2 and every 8 weeks thereafter (applicable to ovarian cancer patients only). For Group 8 patients this assessment should stop at the end of cycle 5.
  - Tumour assessments (CT or MRI scans of chest, abdomen and pelvis for breast cancer and abdomen and pelvis for ovarian cancer with other regions as clinically indicated for the assessment of disease). For Group 8 patients this assessment should stop at the end of cycle 5.

[figure not shown]
Additional assessments for Groups 2, 3, 4, 5, 5.1.....6 and 7 include:

- Blood sampling for determination of AZD2281 plasma concentration at the following timepoints: Pre-dose, 0.25, 0.5, 1, 1.5, 2, 3, 4, 6, 8, 10, 12 hours after dosing at:
  - Group 2 – Day 8 and Day 15
  - Group 3 to 7 – Day 1
- Blood sampling for determination of AZD2281 plasma concentration at the following timepoints: Pre-dose and 1 hour after morning dose
  - Groups 3 to 7 – Day 8 and Day 15
- Blood sampling for determination of AZD2281 plasma concentration at the following timepoints: immediately prior to the first dose of the day and post the first dose of the day between 0 - 0.5 hours, 0.5 to 1.5 hours, 1.5 - 3 hours, 3 - 6 hours, 6 - 8 hours and 8 - 12 hours
  - Group 3 to 5 – Day 29
  - Group 6 and 7 – Day 29 and Day 57

Additional assessments for Group 8 include:

- Blood sampling for determination of AZD2281 plasma concentration for each dose schedule at the following timepoints:  
od schedule:
  - Day 1: pre-dose, 0.25, 0.5, 1, 1.5, 2, 3, 4, 6, 8, 10, 12, 24 hours after dosing
  - Day 8: pre-dose, 0.25, 0.5, 1, 1.5, 2, 3, 4, 6, 8, 10, 12, 24 hours after dosing
  - Day 57: pre-dose, 0 - 0.5, 0.5 - 1.5, 1.5 - 3, 3 - 6, 6 - 8, 8 - 12 hours after dosing

bd schedule:

- Day 1: pre-dose, 0.25, 0.5, 1, 1.5, 2, 3, 4, 6, 8, 10, 12 hours after dosing
- Day 8: pre-dose, 0 – 0.5, 0.5 – 1.5, 1.5 – 3, 3 – 6, 6 – 8, 8 – 12 hours after dosing
- Day 57: pre-dose, 0 – 0.5, 0.5 – 1.5, 1.5 – 3, 3 – 6, 6 – 8, 8 – 12 hours after dosing

tds schedule:

- Day 1: pre-dose, 0.25, 0.5, 1, 1.5, 2, 3, 4, 6, 8 hours after dosing
- Day 8: pre-dose, 0 – 0.5, 0.5 – 1.5, 1.5 – 3, 3 – 6, 6 – 8 hours after dosing
- Day 57: pre-dose, 0 – 0.5, 0.5 – 1.5, 1.5 – 3, 3 – 6, 6 – 8 hours after dosing

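### Group 8 PFS censors survivors at the last scan, near week 16, but counts later deaths as events, so one captured late death takes an arm's Kaplan-Meier curve to zero

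*Protocol*

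**What the plan says.** Three rules in Section 12.3.3 meet in Group 8.

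- **Scan stop.** "Tumour assessments for Group 8 patients should be stopped after Cycle 5 (week 16". Section 7.2.2.3 says "For Group 8 patients this assessment should stop at the end of cycle 5", and Section 7.3.5.5 and Table 7 footnote h also stop Group 8 scans after Cycle 5.
- **Censoring.** A patient alive without progression at the analysis is censored at the last evaluable tumour assessment.
- **Deaths.** Death from any cause without progression is an event. Actual dates are used even when earlier assessments are wholly missing, and "This also applies to patients who die in the absence of progression".

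The Group 8 statistical methods in the synopsis state that "PFS will be summarised using Kaplan-Meier estimates over time and will be displayed graphically".

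Other text does not fit the stop. Section 12.3.3 requires imaging to continue to objective progression in the sentence just before it ends Group 8 imaging. Footnote h sets the general rule, "follow-up tumour assessments will be performed every 8 weeks (+/-1 week) until disease progression or study end", gives the Group 8 stop in brackets, and then adds "Patients must be followed until progression regardless of whether study treatment is discontinued or delayed". The efficacy half of the Group 8 closure criterion in Section 10.5 is "all Group 8 patients have progressed as per RECIST or AstraZeneca has determined that sufficient efficacy data has been collected".

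**The concern.** Survivors and non-survivors are treated differently once scanning ends. A progression-free survivor leaves the risk set at the last scan. A patient who dies later stays in it until death. A patient is therefore still at risk after week 16 only because a death was recorded afterwards, so the censoring depends on the later outcome. The Kaplan-Meier method does not allow for that.

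Late deaths can reach the analysis. Group 8 safety data are collected for up to 12 cycles, subject to sponsor discretion (Section 10.5). Section 7.3.3.7 requires reporting of deaths on study or within 30 days of the last dose, and documents those from disease progression on the CRF. Progression after week 16 is not looked for by scheduled scan, and after Cycle 6 the investigator's response assessment is not entered in the database. A death from unrecorded progression would therefore count as a death without progression.

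At stake is the Group 8 PFS display. Beyond week 16, the four schedules' curves would reflect how many late deaths happened to be captured in arms of about 15, not progression.

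**Working it through.** **1. The protocol's own timing.** Section 10.5 gives "1 cycle being 28 days". Five cycles are 5 × 28 / 7 = 20 weeks; week 16 is 16 × 7 / 28 = 4 cycles. Scans every 8 weeks fall at weeks 8, 16 and 24, so week 16 reproduces as the last scheduled scan before the end of Cycle 5, but not as the end of Cycle 5. Safety collection for 12 cycles runs to 12 × 28 / 7 = 48 weeks. Arm size is 60 / 4 = 15.

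**2. The mechanism, with no assumed rates.** Take 15 patients: 5 progress by week 16, 9 are alive and censored at week 16, and 1 dies at week 30.

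- Week 16: 1 − 5/15 = 0.667.
- Week 30: one patient at risk, one event, so 0.667 × (1 − 1/1) = 0.000.

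Nine of the 15 never had an event. With 8 censored and deaths at weeks 30 and 40, the curve runs 0.667, then 0.667 × (1 − 1/2) = 0.333, then 0.333 × (1 − 1/1) = 0. In general the last late death always meets a risk set of one, so the curve ends at zero whatever the true PFS.

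**3. How many patients are exposed (assumption).** Section 4.2 says median time on treatment before progression approached 6 months in earlier studies. Using 26 weeks as an exponential PFS median:

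- S(16) = exp(−ln 2 × 16/26) = 0.653, about 10 of 15 per arm.
- For medians of 20 and 30 weeks, S(16) = 0.574 and 0.691.
- True PFS at week 48 under 26 weeks: exp(−ln 2 × 48/26) = 0.278.

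**4. Chance that an arm is affected (assumption).** The documents give no late-death risk. Let p be the chance that a patient progression-free at week 16 has a captured later death without recorded progression. Then P(at least one in 15) = 1 − (1 − S(16) × p)^15.

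| p | median 26 weeks | medians 20 to 30 weeks |
|---|---|---|
| 5% | 39% | 35% to 41% |
| 10% | 64% | 59% to 66% |
| 20% | 88% | 84% to 89% |

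Simulation (4,000 arms, scans at weeks 8 and 16) gave 39/63/87%. Every arm with a late death ended at zero.

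**5. Medians.** With no late deaths counted, a median is reached by week 16 only if at most 7 of 15 are progression-free: P(Binomial(15, 0.653) ≤ 7) = 11%. Those medians are genuine. With late deaths counted, a median is reached with probability 1 − Σ P(k) × (1 − p)^k over k = 8 to 15, where P(k) is the probability that k of 15 are progression-free at week 16. This gives 47/69/90%. The excess is 36/58/79 percentage points (37/59/80 from simulation). Where the curve stood above 0.5 at week 16, the simulated median was a late-death date, typically at 27 to 31 weeks for these risks.

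**The case against.** The strongest reply is that the effect is conditional and the endpoint modest. It needs a captured death after week 16 without recorded progression. Capture is limited: Table 7 has no visit after the 30-day follow-up, and entry requires ECOG 0–1 and life expectancy of at least 16 weeks. Symptom-prompted imaging can still record progression (Section 7.3.5.5), and all Group 8 data enter the database through Cycle 6, so the risk set need not be made up only of future deaths. Group 8 PFS is descriptive, with no test, promised median or planned comparison with Group 6. Section 12.4.5 names change in tumour size as the activity measure. Display details can be left to the SAP.

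Much of this stands and limits the severity. It does not remove the defect. The event, censoring and dating rules are fixed in the protocol, so an SAP that follows them reproduces the artefact. Unscheduled imaging is a weak safeguard: the CA-125 rise that triggers an extra scan is itself no longer scheduled after Cycle 5 (Section 7.3.5.6).

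A reader might also infer that database closure is blocked, because RECIST progression cannot be seen after scanning ends. The text does not support that: a sponsor decision that efficacy data suffice is an explicit alternative. Nor does footnote h omit the Group 8 exception; it states the stop and then leaves a general sentence that conflicts with it.

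**Conclusion.** The point holds in conditional form. The Group 8 PFS rules do not match the scan schedule, and one captured late death takes an arm's curve to zero regardless of true PFS, barring unscheduled scans. That step rests only on the stated rules. The frequency, about 39/64/88% of arms, rests on the assumed 26-week median and assumed late-death risks of 5/10/20%.

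Two stronger readings should be resisted. The curve is not bound to reach zero: with no captured late death it ends near week 16, at about 0.65 under the assumed median. And not every reported median would be spurious, since about 11% of arms reach one genuinely by week 16.

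This is a should-fix matter in a descriptive secondary variable. The primary safety objective is untouched. The wording on scan duration, cycle number and the RECIST closure alternative is inconsistent but does not prevent closure.

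**What to change.** In Section 12.3.3, add a Group 8 rule:

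- Limit PFS to the scheduled scan period (week 16 plus the 1-week window). Progression or death within it is an event.
- Censor everyone else, including patients who die later, at the last evaluable scan, and list the later deaths separately.
- Report progression-free proportions at weeks 8 and 16 with confidence intervals, and give no estimate beyond the scan period.

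Reconcile the text:

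- Mark the general sentences on imaging and follow-up to progression (Section 12.3.3 and Table 7 footnote h) as not applying to Group 8 after the scan stop.
- State whether the stop is week 16 or the end of Cycle 5, which is week 20.
- Reword the RECIST alternative in the Group 8 closure criterion (synopsis and Section 10.5), since scheduled scans cannot show it for patients progression-free at week 16.

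The cost is wording in the protocol, carried into the SAP. No extra scan, visit or patient is needed. The sponsor gives up only PFS estimates beyond week 16, which the scan schedule cannot support.
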